10.10. Insurance

The Sponsor must provide insurance or must indemnify (legal and financial coverage) the Investigator/the institution against claims arising from the study, except for claims that arise from malpractice, negligence, or non-compliance with the protocol.

10.11. Report and Publication

After completion of the study, a clinical study report will be prepared according to the ICH Guideline for Structure and Content of Clinical Study Reports (ICH E3) by [REDACTED] in close collaboration with the Investigator and the Sponsor.

All information supplied by the Sponsor in connection with this study and all information generated during this study will remain the sole property of the Sponsor and is to be considered confidential information. No confidential information will be disclosed to others without obtaining prior written consent from the Sponsor and will not be used except in the performance of this study.

If a PI wishes to publish results from this clinical study, written permission to publish must be obtained from the Sponsor in advance. As some of the information regarding the IMP and development activities at the Sponsor may be of a strictly confidential nature, the Sponsor must first review any publication manuscript, including abstracts, prior to their submission to journals, meetings, or conferences. No submission to any journal, meeting or conference or the like, or any kind of publication or disclosure in any form may be undertaken without the prior written approval by the Sponsor.

The Sponsor may choose to publish or present data from this study. Authorship will follow ICMJE guidelines (<http://www.icmje.org/recommendations/browse/roles-and-responsibilities/defining-the-role-of-authors-and-contributors.html>). The Sponsor has the right to use the results for registration and internal presentation and for promotion of the Sponsor's commercial interests.

A/A	Agitation/Aggression
AAPI-CR	Agitation-Aggression Psychiatric Inventory-Clinician Report
ADME	Absorption, Distribution, Metabolism, and Excretion
AE	Adverse Event
BAC	Brief Assessment of Cognition
BDI-II	Beck Depression Inventory – II
BEST	Borderline Evaluation of Severity over Time
BMI	Body Mass Index
BPD	Borderline Personality Disorder
BPDCL	Borderline Personality Disorder Checklist
CGI-S	Clinical Global Impression of Severity
CI	Confidence Interval
CP	Conditional Power
CSP	Clinical Study Protocol
C-SSRS	Columbia – Suicide Severity Rating Scale
DMC	Data Monitoring Committee
eCRF	Electronic Case Report Form
ECG	Electrocardiogram
EoS	End of Study
FAS	Full Analysis Set
IMP	Investigational Medicinal Product
MedDRA	Medical Dictionary for Regulatory Activities
MMRM	Mixed Model for Repeated Measures
MINI	Mini-International Neuropsychiatric Interview
PBMCs	Peripheral blood mononuclear cells
PD	Pharmacodynamics
PK	Pharmacokinetics
PPS	Per Protocol Set
PT	Preferred Term
SAE	Serious Adverse Event

Abbreviation / Acronym	Definition / Expansion
SAF	Safety Set
SAP	Statistical Analysis Plan
SD	Standard Deviation
SOC	System Organ Class
SOP	Standard Operating Procedure
STAI	State-Trait Anxiety Inventory
STAXI-2	State-Trait Anger Expression Inventory 2
STEAE	Serious TEAE
SUSAR	Suspected Unexpected Serious Adverse Reaction
TE	Target Engagement
TEAE	Treatment Emergent Adverse Events
WHO	World Health Organization

1 INTRODUCTION

This document reveals the masked information in the blinded study protocol and may not be made available to Investigators and study-related staff in direct contact with the investigators (e.g., study monitors/CRAs) until general study unblinding.

The analyses described in this SAP are based upon the following study documents:

- Study Protocol, Version 5.0 (March 31, 2023)
- Clinical Study Protocol Addendum – Unmasked Information Version 4.0 (July 23, 2021)
- electronic Case Report Form (eCRF), Study Version 5.0 (June 7, 2022)

This SAP is written to be compliant with the ICH E7 guidelines.

2 STUDY OBJECTIVES

2.1 Primary Objectives

- To investigate the efficacy of vafidemstat in the treatment of agitation and aggression in adult BPD patients
- To investigate the efficacy of vafidemstat in the treatment of adult BPD patients

2.2 Secondary Objectives

- To investigate the effect of vafidemstat in reducing the severity of BPD symptoms in adult patients
- To evaluate the safety of vafidemstat in adult BPD patients

2.3 Exploratory Objectives

- To explore the impact of vafidemstat on functional impairment in adult BPD patients
- To explore the impact of vafidemstat on cognition in adult BPD patients
- To evaluate vafidemstat plasma concentrations (pharmacokinetics) as well as vafidemstat's LSD1-target engagement in peripheral blood mononuclear cells (PBMCs) (pharmacodynamics) after treatment

3 INVESTIGATIONAL PLAN

[figure not shown]
3.1 Overall Study Design and Plan

PORTICO is a double blind, randomized, placebo-controlled, adaptive 14-weeks Phase IIb trial to evaluate the efficacy and safety of vafidemstat in an adult borderline personality disorder (BPD) population.

The study will be an international, multicenter clinical trial conducted in approximately 20 study sites in Europe and the US.

Up to 188 participants will be enrolled and randomized in a 1:1 ratio (94 subjects per arm) to active treatment with vafidemstat (1.2 mg) or placebo to yield an expected 150 study subjects that complete the trial through week 14 (assuming 20% drop out). An interim analysis will be performed to assess treatment response and power to detect differences at the study endpoint after 90 subjects have completed the Week 10 assessment. The sample size may be adjusted upwards based on the outcome of the interim analysis as outlined in section 4.8.

Figure 1. Overall Study Design

(1) During the 2 days off, patients will be taking placebo capsules

Note: An interim analysis will be performed after 90 subjects have completed the *Week 10* assessments.

3.2 Endpoints

The study endpoints are listed below – all information presented in *italics* is masked in the blinded study protocol.

Primary endpoints – Efficacy

- To evaluate the difference on the Clinical Global Impression-Severity focused on Agitation/Aggression (CGI-S A/A) from baseline to *Weeks 8-12*, between the active treatment and the placebo arm.
- To evaluate the difference on the Borderline Personality Disorder Checklist (BPDCL), from baseline to *Weeks 8-12*, between the active treatment and the placebo arm

Secondary endpoints – Efficacy

- To evaluate the change overtime on the CGI-S A/A
- To evaluate the change over time on the BPDCL
- To evaluate the difference on the following measures, from baseline to *Weeks 8-12*, as well as change over time, between the active treatment arm and the placebo arm:
 - a) Borderline Evaluation of Severity over Time (BEST)
 - b) Beck Depression Inventory – II (BDI-II)
 - c) State-Trait Anger Expression Inventory 2 (STAXI-2)
 - d) State-Trait Anxiety Inventory (STAI)

Secondary endpoints – Safety

- To evaluate the following safety endpoints throughout the study, from baseline to week 14, including:
 - a) Number, frequency and severity of Treatment Emergent Adverse Events (TEAEs)
 - b) Number, frequency and severity of Serious TEAEs
 - c) Number and percentage of withdrawn subjects due to TEAEs
 - d) Frequency of physical examination parameters, vital signs and ECG parameters of potential clinical concern throughout the study period
 - e) Frequency of clinical laboratory parameters (hematology, including platelets, and clinical chemistry) of potential clinical concern throughout the study period
 - f) Columbia – Suicide Severity Rating Scale (C-SSRS)
 - g) Use of concomitant medication throughout the study period
- To evaluate the change from baseline to *Week 12* of the following safety endpoints:
 - a) Physical examination, vital signs and ECG parameters
 - b) Clinical laboratory parameters (hematology, including platelets, and clinical chemistry)

Exploratory endpoints

- To evaluate the difference on the following measures, from baseline to *Weeks 8-12*, as well as change over time, between the active treatment arm and the placebo arm:

- a) Columbia – Suicide Severity Rating Scale (C-SSRS)
 - b) Number of visits to healthcare services outside of the trial (primary care, mental health services and ER visits)
 - c) Agitation-Aggression Psychiatric Inventory-Clinician Report (AAPI-CR)
 - d) Brief Assessment of Cognition (BAC) Scale
- To evaluate vafidemstat plasma concentrations (pharmacokinetics) as well as vafidemstat's LSD1-target engagement in peripheral blood mononuclear cells (PBMCs) (pharmacodynamics) after treatment, at baseline, and at weeks 4, 8, and 12

4 STATISTICAL METHODS

4.1 Data Quality Assurance

All tables, figures, and data listings to be included in the report will be independently checked for consistency, integrity and in accordance with standard Pentara procedures.

4.2 General Statistical Considerations

'Baseline' is defined as the last available non-missing pre-treatment assessment. The average of screening and baseline values will be used as the baseline for effectiveness analysis. In the instance where only one value is present that value will be solely used as baseline. Change from baseline is calculated as visit value – baseline visit. 'End of Study' is defined as the last available post-treatment assessment. 'Treatment Day' will be calculated relative to the date of randomization (i.e., Treatment Day = Assessment Date - Randomization Date + 1). For safety summaries, the last pre-treatment measurement is defined as the baseline value.

When duration is calculated for an event (e.g., Adverse Events) and starting and ending date and time are both available, then, duration will be calculated as 'End datetime' – 'Start datetime' and presented in outputs in X day(s) hh:mm format. If time is missing or partially missing for either the end or the start of the event, then, duration will be calculated in days instead as 'End Date' – 'Start Date' + 1 Day.

Continuous data will be summarized in terms of the mean, standard deviation (SD), median, minimum, maximum, and number of observations, unless otherwise stated. The minimum and maximum will be reported to the same number of decimal places as the raw data recorded in the database. The mean, median, lower quartile and upper quartile will be reported to one more decimal place than the raw data recorded in the database. The SD will be reported to two more decimal places than the raw data recorded in the database. In general, the maximum number of decimal places reported shall be four for any summary statistic.

Categorical data will be summarized in terms of the number of subjects providing data at the relevant time point (n), frequency counts and percentages. Any planned collapsing of categories will be detailed in the SAP text and the data displays.

Percentages will be presented to one decimal place. Percentages will be calculated using 'n' as the denominator, unless otherwise stated.

Clinical rating scales may be summarized both as a continuous and as a qualitative variable, depending on the context.

Changes from baseline in categorical data will be summarized using shift tables where appropriate.

P-values greater than or equal to 0.001, in general, will be presented to three decimal places. P-values less than 0.001 will be presented as "<0.001".

Confidence intervals will be presented to one more decimal place than the raw data and the confidence level will be 95% unless stated otherwise.

All summary statistics will be provided by randomized or actual treatment (per analysis set used, see Section 4.5) and by visit and time point where applicable.

Visit windowing will be applied for analyses using visit categories instead of actual number of days relative to dosing for each assessment. For categorical visit summaries, all visits including early termination assessments and unscheduled visits will be included with the closest scheduled post-baseline visit that includes the effectiveness or safety assessment, based on number of days since Day 0. If multiple assessments, such as an early termination visit and a regular visit both fall within the same visit window, any non-missing effectiveness assessments will be averaged, and a worst-case approach will be used for safety data.

Days will be converted to weeks by dividing by seven. Days will be converted to months by dividing by 30.417. Days will be converted to years by dividing by 365.25. All analyses will be conducted with R v3.3.1 or SAS® v9.4 or later using procedures appropriate for the particular analysis. All data collected during the study will be analyzed and reported unless stated otherwise.

4.3 Software

All report outputs will be produced using R v3.3.1 or SAS® version 9.4 or a later version in a secure and validated environment.

4.4 Study Subjects

4.4.1 Disposition of Subjects

A clear accounting of the disposition of all subjects who enter the study will be provided, from screening to study completion.

This will include the following displays:

- A summary by randomized treatment arm (and overall) showing counts and frequency for the following:
 - Subjects screened, including reasons for screen failure
 - Re-screened subjects
 - Subjects randomized
 - Subjects treated
 - Subjects who completed the study
 - Subjects who are still on treatment (for interim analysis only)
 - Subjects who discontinued the study early, including primary reason for discontinuation
 - Subjects who discontinued treatment early, including primary reason for discontinuation
- The number of subjects screened and randomized will also be displayed by country and center

These summary displays will be using all available data (all subjects). Percentages will be based on the number of subjects randomized.

In addition, the following listings will be produced:

- Informed consent (including any re-consents to updated protocol versions, if applicable)
- Randomization (including date of randomization, treatment randomized to and actual treatment, and whether the blind was broken pre-maturely)
- Treatment discontinuations, including duration of treatment and reason for discontinuation

4.4.2 Protocol Deviations

Major protocol deviations are defined as those deviations from the protocol likely to have an impact on the perceived efficacy and/or safety of study treatments. The impact of major protocol deviations on the efficacy and/or safety results will be investigated by assessing the robustness of the study results and conclusions to the choice of analysis set, both including and excluding data potentially affected by major protocol deviations.

Major protocol deviations and any action to be taken regarding the exclusion of subjects or affected data from specific analyses are defined in the project-specific Protocol Deviation Specification. However, the final decision for exclusions and inclusions will be taken during the Blinded Data Review Meeting (BDRM) before unblinding the database.

The following outputs will be produced:

- A summary of major protocol deviations by randomized treatment arm and overall, including:
 - Number and percentage of patients having at least one major protocol deviation
 - Number and percentage of patients by protocol deviation category (i.e., informed consent, missed assessments, ...)
- Listing of all major protocol deviations
- Listing of all minor protocol deviations
- Listing of all inclusion/exclusion criteria violations

Note that inclusions/exclusion criteria will be included both in the specific listings for inclusion/exclusion criteria deviations and in the listing for the appropriate major/minor classification.

4.5 Analysis Sets

With regard to analysis of data, the following analysis sets are defined:

- **Safety Analysis Set (SAF):** All subjects who received at least one dose of the study IMP or Placebo. Individual data will be summarized as treated.
- **Full Analysis Set (FAS):** All patients enrolled (randomized) in the study. Patients will be analyzed as randomized.
- **Per-Protocol Set (PPS):** All subjects in the FAS without any major protocol deviations* as described in Section 10.9 of the Clinical Study Protocol (CSP) and who also satisfy both of the following constraints:
 1. Have at least completed one CGI-S A/A assessment at *Weeks 8-12*
 2. Have at least completed one BPDCL assessment at *Weeks 8-12*Individuals in the PPS population will be analyzed as treated.

*Important violations of eligibility criteria and other deviations from the protocol will be assessed in cooperation with the Sponsor. Important deviations from the protocol may lead to exclusion of a subject from the PPS (See Blinded data review below).

Primary efficacy analysis will be performed using the FAS. Patients will be analyzed as per randomized treatment. Sensitivity and supplementary analyses will be performed in the FAS. Efficacy will also be tested in the PPS analysis will be for descriptive purposes only.

The safety summaries and analyses will be based on SAF. The PPS may be used for additional safety analysis.

Before database lock, protocol deviation and analysis set outputs will be produced and will be sent to Oryzon for review. Analysis Set classifications will be discussed during the Blinded Data Review Meeting to decide which subjects and/or subject data will be excluded from certain analyses. Decisions made regarding the exclusion of subjects and/or subject data from analyses will be made prior to unblinding and will be documented and approved by Oryzon.

A summary of patients (counts and frequencies) in each analysis set, including reasons for exclusion, will be produced in addition to a listing of analysis set assignments by patient, including any reasons for exclusion.

4.6 Estimands

Summary of primary estimand:

1. In study participants with adult BPD, what is the effect of treatment taken for 12 weeks relative to placebo during the double-blind phase, in the protocol-defined FAS study population as measured by the primary endpoints Clinical Global Impression-Severity focused on agitation/aggression (CGI-SS A/A) and Borderline Personality Disorder Checklist (BPDCL).

2. *Objective*

An estimate of effectiveness which would potentially be supportive of registration. Clinically meaningful effects greater than or equal to 0.2 will be supportive of proof of concept.

3. *Estimand*

- A. The population is the FAS as defined by the protocol's inclusion and exclusion criteria.
- B. Effectiveness is measured using an MMRM to estimate change from baseline over 8-12 weeks in the primary endpoints (CGI-SS A/A and BPDCL).
- C. The treatment evaluated is the randomized treatment as it was assigned to study participants. All types of intercurrent events are incorporated using a treatment policy strategy, which evaluates the randomized treatment as taken including missed or modified treatments, treatment discontinuation, and concurrent treatments. Deaths due to treatment are not expected during the treatment period. A hypothetical strategy will be used to account for the intercurrent event of early study termination to estimate the effect anticipated if all patients had completed the study.
- D. The mean change from baseline between treatment and control arms on the primary endpoints will be estimated over visits associated with 8 -12 weeks of treatment. The study is controlled at a 5% level. The Hochberg correction will be applied. If one endpoint is below the 2.5% level or if both endpoints are below the 5% level of significance the study is declared a success. Intercurrent events that are expected to occur include early treatment discontinuation due to patient choice or due to adverse events both unrelated and related to the medication or study indication (e.g., COVID-19).

4. *Primary estimator and missing data.*

The estimator for the primary estimand is a likelihood-based mixed model for repeated measures (MMRM). The primary analysis will include all available assessments. Individuals with no post-baseline information will have the first post-baseline visit imputed. Individuals reported to drop out for lack of efficacy will be given the baseline placebo mean. Individuals reported as dropping out for any other reason will be given the baseline group mean of their corresponding treatment.

5. *Sensitivity analyses and missing data.*

To assess the effect of averaging efficacy for visits corresponding to weeks 8-12 on the primary outcome, a sensitivity analysis will be implemented in which the primary efficacy analysis will be run for visits associated with weeks 8, 10, and 12 separately. As clinical studies are limited in the ability to schedule visits on the exact prespecified study day a continuous time model that extracts the predicted estimates on the prespecified study day will be used as a sensitivity model to assess the degree to which windowing affects the outcome. Additional sensitivity models will be run with multiple imputation within each treatment arm. The first analysis (missing at random; MAR) is meant to estimate the treatment effect if all study participants continued on their current trajectory within the treatment group by imputing the missing data within associated treatment groups. The second analysis (missing not at random; MNAR) imputation is performed for all study participants relative to the placebo group only. This analysis assumes study participants at dropout progress similarly to the placebo group. This analysis will provide a lower bound estimate of the effect. A tipping point analysis using multiple imputation will also be performed.

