9.4. Determination of Sample Size

The sample size for the study was calculated assuming an estimand of the effect size between active treatment and placebo of 0.51 on both endpoints, considering the placebo effect will not exceed the 30%.

The Phase IIa REIMAGINE trial did not contain a placebo group to further help establish the estimand. Moreover, there is no 'gold standard' measure in BPD clinical development, thus, there is no historical clinical trial data on the COAs proposed in PORTICO to establish a more accurate estimand.

Controlling the overall type I error rate at 5% for the study, both endpoints will be tested at a two-sided alpha of 2.5%. A power of approximately 80% for each endpoint is achieved with 75 patients completing the study in each arm, active treatment and placebo. Accounting for a drop-out rate of 20%, 94 patients (total 188 patients) should be recruited per arm. A sample size adjustment will be considered at the interim analysis (see Section 9.6). The total sample size will not be increased to more than 300 completed patients.

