4.7 Determination of Sample Size

The sample size for the study was calculated assuming an effect size of 0.51 on both endpoints between active treatment and placebo. Controlling the overall type I error rate at 10% for the study, each endpoint will be tested at a two-sided alpha of 5% (equivalent to 2.5% one-sided) considering that a significantly larger decrease compared to placebo in either endpoint will be considered sufficient for study success. A power of approximately 80% for each endpoint is achieved with 62 patients completing the study in each arm, active treatment, and placebo. Accounting for a drop-out rate of 20%, 78 patients (total 156 patients) should be recruited per arm. A sample size adjustment will be considered at the interim analysis (see Section 9.6).

The original sample size adjustment above controls the overall type 1 error rate at 10%. However, to meet the requirements for proof of registration, the alpha was adjusted to control for a type 1 error rate of 5%, split evenly between the two endpoints. Assuming an effect size of 0.51 (mean 510, standard deviation 1000) a sample size of 150 completers (75 per arm) is required for 80% power at a two-sided alpha of 0.025 for each endpoint. Assuming 20% dropout would require 188 patients enrolled.

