5.1.1.1 Sensitivity Analysis

Sensitivity analysis for the CGI-S A/A will focus on the following areas:

Estimate over 8-12 week visits

To assess the degree to which estimating across visits represents the overall effect observed, the primary analysis will be repeated for visits 8, 10, and 12 separately. The combined estimate approach will be revisited if the individual visit analyses are not directionally consistent or if this approach is determined to change the direction of the outcome effect, i.e. one visit is driving the overall effect in the primary analysis (ex: one visit significantly favors treatment, while the other two show no effect or favor placebo).

Analysis Population

The primary analysis will be repeated using the PPS for descriptive purposes only.

Missing Values: Multiple Imputation

To conduct further sensitivity analysis intercurrent events like discontinuation of treatment or patient withdrawal, will be imputed. The PROC MI procedure in SAS will be used to do predictive mean matching using linear regression models ([2]). Imputation will be performed after window mapping. The data at each week will be predicted only using data from the previous weeks. The following SAS model will be used:

```
proc mi data=manual nimpute=30 out=MI1 seed= 123456;
  class trt;
  var trt baseline week2 week4 week6 week8 week10 week12;
  fcs regpmm (week2 = baseline trt baseline*trt /details);
  fcs regpmm (week4 = baseline trt baseline*trt week2 week2*trt /details);
  fcs regpmm (week6 = baseline trt baseline*trt week2 week2*trt week4 week4*trt
/details);
  fcs regpmm (week8 = baseline trt baseline*trt week2 week2*trt week4 week4*trt
week6 week6*trt /details);
  fcs regpmm (week10 = baseline trt baseline*trt week2 week2*trt week4 week4*trt
week6 week6*trt week8 week8*trt /details);
  fcs regpmm (week12 = baseline trt baseline*trt week2 week2*trt week4 week4*trt
week6 week6*trt week8 week8*trt week10 week10*trt /details);
run;
```

Here, baseline is the baseline measurement, and week x is the result of the measurement for Week x . Trt is an indicator variable for the received treatment.

Imputed values that fall outside of the possible range of the test variable will be set to the min or max possible score for the test before imputation.

The following simplifications will be attempted if the model fails to converge for any reason:

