1. Only the results from the directly preceding visit and baseline will be used in each of the models (i.e., Week 10 values will be predicted using Week 8 and baseline measurements)
2. Only baseline and baseline*trt will be used in each prediction model

Change from baseline to *Weeks 8- 12* will be calculated for each of the 30 simulated datasets. The main analysis model described in 5.1.1 will be run for each simulated dataset and the values will be aggregated using PROC MIANALYZE. In addition to the estimates for the contrast between treatments at *Weeks 8- 12* (including confidence intervals and p-values), the composition of the total variance in parameter estimation will be broken down by variability between datasets and variability within datasets.

This analysis above will be performed using the entire dataset for imputation across treatment as well as imputation based on the placebo group only.

A tipping point analysis as implemented in Ratitch et al. [3] will also be run. This analysis finds a tipping point across a spectrum of assumptions underlying the missingness of the data (from less conservative to more conservative) in which the conclusion of the study changes from favoring the treatment group to being unfavorable.

Impact of Covariables

The impact of additional covariables will be investigated by including them in the main model, including interactions with Visit and Treatment Arm, as well as the triple interaction between the covariable, Visit and Treatment arm.

The following covariables will be considered:

- Country or center (if number of patients per center allows)
- Psychotherapy at baseline (the main effect is already part of the standard model, so only the interactions need to be added for sensitivity)
- Sex

Other demographic variables may be investigated for sensitivity analysis if there is a reason to suspect an imbalance between treatment arms.

These covariables will be tested by including only one covariable (and interactions) at a time, not all at once. F-tests will be performed for the main effect as well as interactions. In case of highly significant interactions further analysis will be considered. This sensitivity analysis will be performed using the FAS.

Model Assumptions

As described in Section 5.1.1 the assumptions of the mixed model will be investigated visually by the statistician. Regardless of the outcome of this investigation, at least the following sensitivity analyses will be performed:

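### SAP 4.6 calls the placebo-based imputation a lower bound on the effect; it is a conservative reference-based scenario, and the true effect can lie below it

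*SAP*

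**What the plan says.** SAP 4.6, in its item on sensitivity analyses and missing data, plans two multiple-imputation analyses. The first imputes within each arm under missing at random. In the second, "imputation is performed for all study participants relative to the placebo group only". The assumption is stated openly: "This analysis assumes study participants at dropout progress similarly to the placebo group". The SAP then adds, without any condition: "This analysis will provide a lower bound estimate of the effect". The sentence after that plans a tipping-point analysis.

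SAP 5.1.1.1 gives the mechanics: "The data at each week will be predicted only using data from the previous weeks". The SAS code enters baseline and every earlier week as predictors. The procedure is to be run twice, with "imputation across treatment as well as imputation based on the placebo group only".

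Protocol 9.4 expects some improvement on placebo. The effect size was set "considering the placebo effect will not exceed the 30" per cent, although neither the base of that percentage nor its size in SD units is given.

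**The concern.** A lower bound is a value that the true effect cannot fall below. Giving active-arm dropouts a placebo-like course removes the drug's benefit from them but leaves them whatever improvement placebo patients show. Conditioning on their own earlier visits also carries forward part of any benefit recorded before they left. The result is a bound only if no group of active dropouts does worse than comparable placebo patients. Neither document argues this, and the reasons for leaving listed in Protocol 4.2 and 6.1.1 include adverse events, suicide risk and an emergent need for psychotherapy.

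What is at stake is how the sensitivity result is read. SAP 4.6 treats an effect of 0.2 or more as supporting proof of concept and has registration in view. A reader who sees a figure labelled as a lower bound will set it against 0.2 and may conclude that missing data cannot take the effect any lower.

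**Working it through.** **Inputs.** Completer effect D = 0.51 SD, dropout d = 20%, 75 completers per arm and 188 enrolled (SAP 4.7; Protocol 9.4); 94 per arm (SAP 3.1). The placebo response P, in SD units, is not in the documents and is assumed. Improvement is counted as positive.

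**1. Reproduce the plan's figure.** The target is "80% power at a two-sided alpha of 0.025 for each endpoint". By the normal approximation, n per arm = 2(2.241 + 0.842)² / 0.51² = 73.1, rounded up to 74. The exact t calculation gives 75. Power at 75 per arm is 81.1% (normal) or 80.4% (t). Enrolment is 150 / 0.8 = 187.5, rounded up to 188. The planning inputs reproduce. The lower-bound sentence carries no figure of its own.

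**2. Placebo-mean value.** If active dropouts take the placebo mean, the effect is (1 − d) × D = 0.8 × 0.51 = 0.408.

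**3. Active dropouts s SD worse than placebo.** The effect is (1 − d)D − d × s = 0.408 − 0.20s.

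- Each 1 SD of shortfall costs 0.20 SD: s = 1 gives 0.208.
- The effect reaches 0.2 at s = (0.408 − 0.2) / 0.2 = 1.04, and zero at s = 0.408 / 0.2 = 2.04.

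**4. Illustration with an assumed placebo response.** Active dropouts end with no change while placebo dropouts keep P, so s = P.

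| Assumed P (SD) | True effect | Below 0.408 by |
|---|---|---|
| 0.2 | 0.368 | 0.04 |
| 0.5 | 0.308 | 0.10 |
| 0.8 | 0.248 | 0.16 |

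**5. Both arms lose the response.** At equal 20% dropout, 0.8(P + 0.51) − 0.8P = 0.408 for any P, so there is no gap against the simple value. At 30% active and 10% placebo dropout with P = 0.5, the result is 0.7 × 1.01 − 0.9 × 0.5 = 0.257, against a placebo-mean value of 0.7 × 0.51 = 0.357.

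**6. Effect of conditioning on earlier visits.** A simulation of sequential placebo-only imputation (40,000 per arm; assumed correlations and dropout times; no baseline covariate; normal residuals in place of predictive mean matching) returned about 0.46.

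- With missing at random true, the true effect was about 0.51, so the method is conservative against that.
- With active dropouts truly at the placebo mean, the true effect was about 0.43. This exceeds 0.408 because some simulated dropouts still had observed visits in Weeks 8 to 12.
- With active dropouts returning to baseline, it was about 0.38, 0.35 and 0.31 for P = 0.3, 0.5 and 0.8.
- With both arms returning to baseline, it was 0.42 to 0.43.

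In this set-up the imputed value lay above the truth even when the placebo assumption held on average, because early benefit was carried forward.

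**The case against.** The strongest reply rests on the estimand. SAP 4.6 handles early termination by a hypothetical strategy that asks what would have happened had everyone completed. For that question, giving active dropouts no drug benefit is a natural conservative end, and in context the phrase may mean only the lower of the two imputation analyses. That is a fair account of why the analysis was chosen, and calling it conservative stands. It does not make the sentence true, since the result is a bound only if staying on drug could not have left these patients worse than placebo.

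The next reply is that the tipping-point analysis already probes worse cases. That also stands, and it limits the harm. SAP 5.1.1.1 describes it as moving from milder to harsher assumptions, though without a shift range or step. It is a separate analysis and does not turn the placebo-based one into a bound.

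Third, the size is modest. At P = 0.2 to 0.5 the gap of 0.04 to 0.10 SD is below one standard error of the effect, √(2/94) = 0.146 SD. Only the P = 0.8 case, at 0.16, slightly exceeds it.

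Two stronger readings are tempting, and the documents support neither.

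- A reader might infer that the primary rule for patients with no data after baseline, which assigns a baseline mean, is already harsher than this analysis. It fills only the first visit after baseline (SAP 4.6 and 5.1.1). Weeks 8 to 12 are left to the mixed model, which uses the patient's own arm.
- A reader might infer that the claimed bound is routinely too high by 11% to 65% (0.04/0.368 to 0.16/0.248). That needs active dropouts to lose all improvement while placebo dropouts keep theirs, and a P that the documents do not give. The protocol's 30% has no stated base and cannot supply it.

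**Conclusion.** The concern holds as a correction to what SAP 4.6 claims for this analysis. Placebo-based imputation conditional on earlier visits is a conservative reference-based scenario, not a lower bound.

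The firm result is the sensitivity: at 20% dropout, 0.20 SD of effect is lost for each 1 SD by which active dropouts fall short of placebo, starting from 0.408. The 0.04 to 0.16 SD range is illustrative only, resting on an assumed placebo response and on loss in the active arm alone. The simulated 0.46 depends on its assumed correlations and dropout times.

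The point bears on how one sensitivity result is interpreted. It does not touch the primary analysis, the sample size or the success rule. Nor do the documents show that the study report would present this figure as the least the drug could do: SAP 5.1.1.1, which lists the outputs, does not repeat the label.

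**What to change.** In SAP 4.6, replace the lower-bound sentence with one that describes the analysis as *a conservative, reference-based estimate assuming dropouts follow the placebo course*.

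Take the worse-than-placebo cases from the tipping-point analysis that is already planned. State its shift range and step in SAP 5.1.1.1, and have the shifts for active-arm dropouts extend below the placebo course. A separate run in which active-arm dropouts return to their own baseline and placebo dropouts follow placebo is optional. It would give one concrete pessimistic effect estimate, which a tipping point alone does not.

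The cost is a wording change and a stated range, plus one further imputation run with existing code if the optional analysis is added. The downside for the sponsor is that the most pessimistic figure reported will be less favourable.
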